1.8 Primary Specimen Collection

A. *What types of specimen will be collected, where, and by whom?*

We will utilize a urine or saliva screen that tests for buprenorphine and methadone (to provide corroboration of MAT engagement and compliance) and additional substances (e.g., benzodiazepines, barbiturates, cocaine, marijuana, methamphetamine, morphine, oxycodone, phencyclidine and amphetamine). These specimens will be collected by study research assistants at baseline and each follow-up time point (8-weeks and 16-weeks).

Biochemical verification of self-report opioid relapse and other drug use is the gold standard measurement of drug use and, without biochemical verification, self-reported drug use as an outcome variable will be questioned by the scientific community.

B. *How will the specimens be transported and by whom?*

The sample will be collected and results read at the time of sample collection. The sample will be disposed as soon as results are read (typically within 10 minutes of sample collection) and recorded. The sample will not be transported. Samples will be collected and read in a private area where others will not be able to see or hear the results.

C. *Who will process the specimens?*

Research assistants will process the sample.

D. *How long will the specimens be kept?*

The sample will be disposed of immediately after results are read and recorded.

E. *How will the specimens be destroyed upon study completion?*

Samples will be flushed down the toilet (urine test) or disposed of in the trash (saliva test).

F. *If specimens will be banked for future use, what will be the process for providing investigators with access to the bank and how will this be tracked?*

N/A

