1.9 Interviews, Focus Groups, or Surveys

A. Administration

■ Timing and Frequency

Research staff will collect interview data and drug screens from both intervention and control group subjects through face-to-face standardized measures conducted at baseline and either phone or face-to-face measures 8- and 16- weeks post baseline. Cognitive testing data will be collected at baseline and 8-weeks. If the research assessments are conducted over the phone, cognitive assessments and drug screen results will be considered missing data. Additionally, subjects will engage in twice-daily EMA assessments of approximately 3-5 minutes each. Subjects will also initiate EMA communications to report lapses or serious cravings, which will also last for under 5 minutes.

■ Location

The assessments and drug screens will take place in private rooms at the New Brunswick Counseling Center (NBCC) and Lennard Clinic.

■ Procedures for Audio and Visual Recording

Audio or video recordings will be made of the MORE therapy sessions and the recordings will be transcribed research staff. All recordings will be stored in password protected computers, in a locked office at [name], in password protected files, on the Rutgers network.

B. Study Instruments

Feasibility Outcomes:

- The number of individuals who express interest in the study and the number who refuse (and reasons for refusal) will be tracked in a log.
- The number of individuals who contact the staff with interest in the study will be tracked in a log.
- The number of individuals screened and eligible/ineligible will be tracked in a log.
- The number of individuals consented will be tracked in a log.
- The number of individuals who refuse participation after/during consent process will be tracked in a log.
- The number of sessions completed by study participants will be tracked in a log.
- The number of participants who drop out and reasons for drop out will be tracked in a log.
- Reasons for missed sessions will be tracked in a log.
- The number of completed/missed assessments will be tracked in a log.

Exploratory outcomes among participants in the MORE condition relative to treatment as usual (TAU) in regard to opioid use outcomes such as:

- Time until first opioid lapse assessed through ecological momentary assessment data and timeline follow-back.

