Data will be received by the REDCAP system. Data access between the REDCap database and the web server is encrypted and restricted to a monitored port. All REDCap data, which is displayed or captured by the user interface, is encrypted for security. Within REDCap all data transactions including inserts, updates, deletions, import/export and reporting are logged. The EMA system in this study deployed via REDCap will reside in a HIPAA compliant protected space. The REDCap production and development servers use encrypted drives. Physical hardware will be secured in a locked facility.

The data will only be accessible to study investigators and staff. The data will be processed by an already developed REDCap program that formats the data as a "long file" with one row per time point per individual participant. The investigators will employ linear mixed models to test the effects of MORE vs. the control condition on substance use, craving, pain, and other study variables. The treatment X time interaction will be the main fixed effect of interest. Models will include a random intercept, as well as a random slope if warranted by model fit statistics. Auto-correlation between repeated measures will be modeled as a first-order autoregressive function. We will also compute within-group linear mixed models examining mindfulness practice duration as a predictor of clinical outcomes.

Substance use history (Baseline). We will use the PhenX Toolkit-Substance Abuse and Addictions Core Tier 1 Collection² to gather self-report information on lifetime use of opiates, alcohol, tobacco and substances, and past-30 day use of all substances.

Current substance use (Baseline, 8 weeks, and 16 weeks). We will utilize a urine screen that tests for buprenorphine and methadone (to provide corroboration of MAT engagement and compliance) and additional

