substances (benzodiazepines, barbiturates, cocaine, marijuana, methamphetamine, morphine, oxycodone, phenyclidine and amphetamine). At each research visit we will conduct a timeline follow-back³ with each participant to account for missing EMA drug use data. The timeline follow-back is a reliable and valid measure where participants are asked to recall and record events (e.g., drug use) within a specified time period on a calendar. We will combine self-report of opioid relapse and other drug use with biochemical measures because it is the gold standard, and without biochemical verification, self-reported drug use as an outcome variable will be questioned by the scientific community. If a biochemical measure is negative, but the participant reports drug use, the participant will be coded as using drugs since the biochemical measure will only capture a specific time point. However, if the participant self-reports drug abstinence, but the biochemical measure is positive for drug use (the more likely scenario) the participant will be coded as having used drugs.

Craving (Baseline, 8 weeks, and 16 weeks). Opioid and other drug craving will be assessed with an adapted version of the Penn Alcohol Craving Scale (PACS)⁴ and the Craving Suppression Scale. The PACS is a valid, reliable, and internally consistent measure that consists of five self-report items that have been found to predict relapse. The items assess the intensity, frequency, ability to resist, and duration of craving. Originally developed to assess alcohol craving, it has been adapted and used to measure craving for various substances, including opioids,⁵ and adapted versions have been used in trials of mindfulness-based interventions for substance use.⁶ The Craving Suppression Scale is a 17 –item measure that assesses how individuals cope with craving

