Cognitive impairment, psychosis, suicidality (screening). To determine study eligibility, cognitive impairment will be assessed with the Mini Mental Status Exam,¹⁵ psychosis will be assessed with the Structured Clinical Interview for DSM-V (SCID) Psychotic screen,¹⁶ and suicidality will be assessed with the Ask Suicide Screening Questions Tool. The MMSE is a widely used valid and reliable measure of cognitive functioning that assesses orientation to time and place, registration, attention and calculation, recall, language, Scores <24 indicate cognitive impairment. The SCID Psychotic Screen is a semi-structured clinical interview that assesses symptoms of psychotic disorders (e.g., delusions, hallucinations) based on the DSM-V criteria. The ASQ is a five item screening tool that is part of the NIMH toolkit.¹⁷

Mental health history (Baseline) and psychiatric symptoms and treatment (Baseline, 8 weeks, 16 weeks). At baseline, history of mental illness and psychiatric treatment will be assessed. At each subsequent research visit, participants will be asked if they took any psychotropic medications or received any mental health counseling since their last visit. At each research visit, symptoms of depression and anxiety will be evaluated with the Center for Epidemiologic Depress Scale and the Beck Anxiety Inventory.

Physical health history (Baseline) and symptoms (Baseline, 8 weeks, 16 weeks) and pain medication (baseline, 8 weeks, 16 weeks). At Baseline, history of illness such as HIV, cancer, heart disease, emphysema, asthma and other chronic conditions will be assessed. Daily health functioning will be evaluated at every research visit with the RAND 36-Item Health Survey 1.0 (SF-36).²⁰ The reliability and validity of this self-report scale that measures overall health and ability to complete daily activities has been shown. Current pain medication (prescribed and over the counter) will be assessed at each research visit.

Savoring (Baseline, 8 weeks, 16 weeks). Savoring will be measured by the Savoring Beliefs Inventory (SBI). The SBI is a reliable and valid scale that consists of 6 items that assess individuals' perceptions of their ability to derive pleasure through anticipating upcoming positive events, savoring positive moments, and reminiscing about past positive experiences

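### The drug-use coding rule makes no exception for prescribed drugs, so a participant prescribed a drug on the screening panel may be miscoded as using at screened in-person visits

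*Combined protocol and SAP*

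**What the plan says.** Section 1.9 B, under Current substance use, combines self-report with a drug screen. Reported use counts as use even if the screen is negative. In the opposite case, "if the participant self-reports drug abstinence, but the biochemical measure is positive for drug use", the result is that "the participant will be coded as having used drugs". The protocol expects this second case to be the commoner one. No exception is written into it.

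Sections 1.8 A and 1.9 B give the panel. Apart from methadone and buprenorphine, which are tested to corroborate treatment, it covers "benzodiazepines, barbiturates, cocaine, marijuana, methamphetamine, morphine, oxycodone, phencyclidine and amphetamine".

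Section 1.9 B also collects medication data. On pain: "Current pain medication (prescribed and over the counter) will be assessed at each research visit". On mental health, at visits after baseline "participants will be asked if they took any psychotropic medications". Neither item is mentioned in the coding rule.

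Section 1.9 A allows follow-up by phone, in which case "cognitive assessments and drug screen results will be considered missing data". The baseline visit is face to face.

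The eligibility criteria in Section 4.2 D require chronic non-malignant pain. They do not exclude people who are prescribed a drug on the panel.

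**The concern.** Some classes on the panel are ordinary prescription medicines, and the trial enrols people with chronic pain. The rule as written gives a participant who takes such a medicine as prescribed, and reports no drug use, the same code as someone concealing illicit use.

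Three consequences follow.

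- **Dilution.** Someone who screens positive from a prescription whether or not they use other drugs cannot show a benefit on a screen-based outcome.
- **Dependence on visit mode.** The same person on the same prescription is coded as using when screened in person and abstinent when interviewed by phone. The coded status changes although the behaviour has not.
- **Carry-over to the next trial.** Drug use appears in hypothesis 3 (Section 1.1 B), and Section 6.1 B says the pilot is meant to give a preliminary effect size for a larger study. Section 1.3 puts that study at N=150.

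**Working it through.** The plan has no figure of its own to reproduce. Sections 1.5 and 6.1 B justify N=31 without an alpha, power or effect size. The check is therefore a reading of the rule, followed by an illustration of size.

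**Step 1: follow the rule for one participant.** Take someone prescribed a benzodiazepine who uses nothing else and reports abstinence.

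| Visit | Screen | Code under Section 1.9 B |
|---|---|---|
| Baseline, in person | positive | used drugs |
| Follow-up, in person | positive | used drugs |
| Follow-up, by phone | missing | abstinent (self-report only) |

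Nothing elsewhere alters these codes. The covariates listed in Section 1.6 A concern methadone-clinic treatment and name neither pain nor psychotropic medication.

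**Step 2: size for a proportion.** Let p be the true proportion using, and f the share of truly abstinent participants who screen positive from a prescription, equal in both arms.

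- Observed proportion = p + (1 − p)f
- Observed difference = true difference × (1 − f)

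The value of f is an assumption. The true rates are also assumed: 50% in TAU, borrowed from the six-month relapse figure in Section 1.2 for illustration only, and 30% in MORE. The sample size per arm uses two-sided alpha 0.05, 80% power, 1:1 allocation and the normal approximation for two proportions.

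| f | TAU observed | MORE observed | Difference | n per arm |
|---|---|---|---|---|
| 0 | 50% | 30% | 20 points | 93 |
| 0.05 | 52.5% | 33.5% | 19 points | 106 |
| 0.10 | 55% | 37% | 18 points | 120 |
| 0.20 | 60% | 44% | 16 points | 152 |
| 0.30 | 65% | 51% | 14 points | 194 |

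**Step 3: number of people.** With half of 31 truly abstinent and everyone screened, the number miscoded at a visit is 31 × 0.5 × f. This is about 0.8, 1.6, 3.1 and 4.7 people for f = 0.05, 0.10, 0.20 and 0.30.

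**Step 4: chance imbalance.** Two more prescription holders in MORE (n=15) than in TAU shift the difference by at most 2/15 = 13 points. That bound is reached only if both are truly abstinent. At 50% abstinence (assumption) the expected shift is 2 × 0.5/15 = about 7 points.

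**Step 5: the named outcomes.** Section 1.9 B says days of use and time to first lapse come from EMA and timeline follow-back, and does not name the screen there. Under Current substance use it says self-report and biochemical measures will be combined. It does not say whether a positive screen on a day of reported abstinence adds a day of use, or what date a lapse would take. Steps 2 to 4 therefore apply directly only to a proportion using at a visit, and the effect on the two named outcomes cannot be computed.

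**The case against.** A reader might infer that chronic-pain patients on prescribed medicines are coded as users at every visit, permanently. The documents do not support that. The medicine must be one the panel detects, which leaves out many pain medicines. The visit must be in person and the screen positive that day. Prescriptions can also start, stop or be taken as needed. Section 1.2 says practitioners are reluctant to prescribe opioid analgesics to people with this history, which argues for a low f for morphine and oxycodone. It says nothing about benzodiazepines, barbiturates or amphetamine.

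A reader might also infer that methadone itself makes everyone a user. Its stated purpose on the panel argues against that intention. The rule only fails to say so.

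The mixed model in Section 1.9 B, with treatment by time as the effect of interest, partly answers the imbalance point. A stable prescription positive at baseline and at follow-up is mainly a baseline difference. It does not remove the dilution, since with constant f the observed change is also the true change times (1 − f). Nor does it help when a screened baseline is followed by a phone visit. The simple group comparisons in Section 6.1 A remain exposed.

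Finally, counting every positive is a conservative choice in an opioid use disorder sample, and letting reported prescriptions cancel a positive weakens the biochemical check that the protocol values. This is a real cost. It is a reason to keep the all-positives coding as a sensitivity analysis.

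**Conclusion.** The point holds in a limited form. Applied as written, the rule can miscode a participant prescribed a panel drug as using at a screened visit, and code the same person as abstinent by phone. For a proportion using, a 20-point difference becomes 19 to 14 points for f between 0.05 and 0.30. That range is an assumption, because the documents give no prescription rate, and it takes f to be equal in the two arms.

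The effect on days of use and time to first lapse is uncertain, because the role of the screen in those outcomes is undefined. The sample sizes in the working show sensitivity only. They do not show that the N=150 planned for the larger trial is wrong.

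Severity is minor to moderate. Drug use is exploratory in an unpowered pilot, and the recruitment, retention and follow-up milestones in Section 1.1 B do not depend on this rule. It is worth correcting because the estimate is meant to inform the larger trial and the change is cheap.

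**What to change.** Amend the coding rule in Section 1.9 B (Current substance use) as follows.

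1. A positive analyte matched by a current prescription, recorded by drug name at that visit among the pain or psychotropic medicines, is not coded as drug use.
2. Positives for methadone and buprenorphine given as treatment do not count as drug use.
3. State how a positive screen enters days of use and time to first lapse: whether it adds a day, what date a lapse takes, or that it does not enter them. Fix this before outcome data are seen.
4. Report the coding that counts all positives (other than treatment methadone and buprenorphine) as a sensitivity analysis.

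**Cost.** A few sentences of text and a small change to data collection. Pain medication is already assessed at each visit. The psychotropic question is described only for visits after baseline and does not say that drugs are named, so it must record names at every visit, including baseline. The main downside is that misuse of one's own prescribed drug would then rest on self-report. The documents also describe no verification of reported prescriptions. The sensitivity analysis shows how much these limits matter. The change concerns outcome coding only and does not touch clinical care.

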In addition, the study will explore outcomes among participants in the MORE condition relative to treatment as usual (TAU) in regard to opioid use outcomes such as:

- Time until first opioid lapse
- Time until MMT dropout
- Total days of methadone treatment
- Total days of opioid or any drug use
- Trajectories of positive and negative affect
- Drug craving
- Pain severity and pain interference
- Inhibitory control, implicit associations, and the precedence of global features in visual perception

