The following cognitive tasks will be completed on a laptop computer. The computer tasks will be administered online through the Inquisit platform. Pre-developed Inquisit scripts exist for each computer task, and participants' encrypted task data will be housed on a secure server "using Secure Sockets Layer (SSL)", the same technology used by online shopping and banking web sites to protect sensitive information transmitted over the web" (<https://www.millisecond.com/support/docs/v5/Inquisit.pdf>). Each task will be scored within the Inquisit platform according to validated scoring methods.

Inhibitory control, Go-No Go Task (Baseline, 8-weeks): To assess inhibitory control, participants are asked to press the Spacebar on a computer when they see, on the computer screen, a green rectangle (=go) but refrain from pressing the Spacebar when they see a blue rectangle (=nogo).²¹ The blue and green rectangles can be vertical or

horizontal. The vertical rectangle has a high probability of being green (a go trial) and the horizontal rectangle has a high probability of being blue (a nogo trial). Participants get information about the orientation of the rectangle (=cue) shortly before the color of the rectangle is revealed. Mean reaction times will be derived from the Go/No-Go tasks.

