Opioid/Natural Reward, Implicit Association Task (IAT; Baseline, 8-weeks): The IAT is a widely-used cognitive-behavioral paradigm that measures the strength of automatic (implicit) associations between concepts in people's minds relying on latency measures in a simple sorting task.²² Participants are asked to, on a computer, categorize attributes (e.g. "pleasant"; "unpleasant") and target items (e.g. "friends" vs. "pills") into predetermined categories via keystroke presses. The basic task is to press a left key (E) if an item (e.g. "pleasant") belongs to the category presented on the left (e.g. "Good") and to press the right key (I) if the word (e.g. "unpleasant") belongs to the category ("Bad") presented on the right. For practice, participants sort items into the target categories "Opioids vs. Natural Reward" and the attribute categories "Good vs. Bad". For the test, participants are asked to sort categories into the paired/combined categories (e.g. "Natural Reward OR Good" on the left vs. "Opioid OR Bad" on the right). Pairings are reversed for a second test (e.g. "Opioid OR Good" on the left vs. "Natural Rewards OR Bad" on the right). Block order is counterbalanced by group number. A d-score will be derived from the implicit association task.

Precedence of Global Features in Visual Perception, Global Local Task (Baseline, 8-weeks): On a computer, participants are briefly presented with letter shapes (e.g. H or S) that are made up of little letter shapes (e.g. H or S).²³ Some of these letters have the same global (overall shape) and local (individual building shapes) letters (e.g. an H that consists of Hs), and some have different global and local letters (e.g. an H that consists of Ss). In the global condition participants are asked to respond to the global shape of the letter (e.g. press key H if the global shape of the letter is an H regardless of individual building blocks); in the local condition participants are asked to respond to the local shapes of the letter (e.g. press H if the local building elements are Hs regardless of overall shape). The number of errors during the last block of the global/local task will provide a shifting attention score.

Intervention implementation (Week 8). Number of sessions completed and missed will be assessed for each participant in both conditions. Reasons provided for missed sessions will also be recorded.

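### The only score named for the Go/No-Go task is mean reaction time, which does not directly measure inhibitory control, and the trials entering it are not stated

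*Combined protocol and SAP*

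**What the plan says.** Section 1.6 B closes its list of exploratory MORE-versus-TAU outcomes with the three constructs measured by the computer tasks: "Inhibitory control, implicit associations, and the precedence of global features in visual perception". Section 1.9 B gives the first of these its instrument: "Inhibitory control, Go-No Go Task (Baseline, 8-weeks): To assess inhibitory control, participants are asked to press the Spacebar". The press is for a green rectangle. On the other trials participants must "refrain from pressing the Spacebar when they see a blue rectangle". Before the colour appears, the rectangle's orientation acts as a cue: vertical makes a go trial likely, horizontal a no-go trial.

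The task description ends with its score: "Mean reaction times will be derived from the Go/No-Go tasks". Nothing states whether the mean is taken over go trials or over all key presses, or whether it is split by cue. No rate of failed no-go inhibition (commission errors) is named for this task anywhere in the document.

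A general sentence ahead of the three task descriptions reads: "Each task will be scored within the Inquisit platform according to validated scoring methods". The other two tasks each have one named score. For the implicit association task: "A d-score will be derived from the implicit association task". For the global/local task: "The number of errors during the last block of the global/local task will provide a shifting attention score". The analysis plan in section 6.1 A adds no definition of any cognitive score.

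**The concern.** A Go/No-Go task assesses inhibition through the trials on which a response has to be withheld. When the participant succeeds, there is no key press and nothing to time. A mean reaction time is therefore built from go presses, from failed inhibitions, or from both, and never from a successful inhibition. A score of this kind chiefly describes how fast people respond.

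The cue makes the gap easier to see. A vertical rectangle invites the participant to prepare a press, and inhibition is tested hardest when that rectangle then turns out to be blue. An unqualified mean reaction time does not isolate those trials.

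At stake is the label on one result. Section 6.1 B says the pilot is meant to give a preliminary effect size and to inform a larger study. If the plan is followed as written, the effect size reported for inhibitory control would largely describe response speed, and could influence the choice of outcome for the next trial.

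**Working it through.** The plan gives no numerical result for this task, so there is no figure to reproduce. The check has two parts.

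**1. Which trials can contribute to the score (section 1.9 B)**

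| Trial | Correct response | Reaction time if correct | Reaction time if wrong |
|---|---|---|---|
| Go (green) | Press | Yes | None (no press) |
| No-go (blue) | No press | None | Yes (commission error) |

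Successful inhibition is the correct no-go cell, and it has no reaction time. The mean can be formed only from correct go presses and commission errors.

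**2. How far the mean can follow inhibition**

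All values here are assumptions for illustration; none comes from the protocol. Take 125 go and 125 no-go trials, every go trial answered, a go reaction time of 330 ms, a proportion *c* of no-go trials on which inhibition fails, and a reaction time *e* on those failures.

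- Go trials only: mean = 330 ms, whatever *c* is.
- All key presses pooled: mean = (125 × 330 + 125*c* × *e*) / (125 + 125*c*) = (330 + *c* × *e*) / (1 + *c*).

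| Failed inhibition, *c* | Go-only mean | Pooled mean, *e* = 280 ms | Pooled mean, *e* = 330 ms |
|---|---|---|---|
| 0% | 330 | 330.0 | 330.0 |
| 10% | 330 | (330 + 28) / 1.1 = 325.5 | 330.0 |
| 50% | 330 | (330 + 140) / 1.5 = 313.3 | 330.0 |
| 100% | 330 | (330 + 280) / 2 = 305.0 | 330.0 |

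The commission-error proportion is *c* itself and spans 0% to 100% down the rows. The go-only mean does not move. The pooled mean moves only when errors differ in speed from correct go presses, and then towards *e*, so both the size and the sign of any shift depend on a quantity the plan does not give. A change in *e* or in go speed would also move the pooled mean with *c* held fixed. The table therefore shows insensitivity and ambiguity; it does not estimate an effect in this trial.

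**The case against.** The strongest reply is the sentence on validated scoring. It covers all three tasks, the Go/No-Go task carries a literature citation, and the platform may well produce an error score. The plan also speaks of mean reaction times in the plural, which could mean one per cue condition, and go reaction time by cue may carry indirect information about response preparation or restraint. Unlike the global/local sentence, the Go/No-Go sentence does not expressly tie its metric to a construct.

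Part of this stands. The documents do not show that errors will be ignored, and it would be too strong to say that reaction time carries no information on inhibition. But the validated-scoring sentence names no metric, and no contrast by cue is specified. One score is named for each task, and an error count is named where one is wanted, for the global/local task. Mean reaction time is thus the natural reading of the intended Go/No-Go score.

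A reader might also infer two further things that the documents do not support:

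- *That careful, slower responders would look worse and impulsive ones better.* The plan never says whether a longer or shorter reaction time counts as favourable, so no direction of bias follows.
- *That the information from withheld trials is lost.* Section 1.9 B says task data are held on a secure server but does not describe their level of detail. Trial-level retention is neither stated nor ruled out.

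The low stakes are also a fair reply. Inhibitory control appears in none of the five hypotheses in section 1.1 B and is not among the preliminary primary and secondary outcomes named in section 1.3. The progression milestones concern recruitment, session attendance and follow-up.

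**Conclusion.** The point holds as a gap in how the outcome is scored. The single score named for inhibitory control does not directly measure inhibition, mainly reflects response speed, and leaves open which trials and cues it uses. This follows from the protocol's own task description: a correct no-go trial yields no reaction time. It rests on one reading, that the score named for each task is the score intended for its construct, which the parallel wording for the other two tasks supports.

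The size is small and cannot be expressed in the trial's own units, since the documents give no trial counts, reaction times or error rates for the task. One exploratory outcome in an unpowered pilot is affected, and no hypothesis or progression decision depends on it. The practical consequence is confined mainly to the preliminary effect size taken into the larger study.

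**What to change.** In section 1.9 B, name the proportion of commission errors on no-go trials as the inhibitory-control score, with particular attention to blue targets that follow the vertical, go-probable cue. Report mean reaction time on go trials, by cue, as a separate speed measure, so that a speed-accuracy trade-off can be seen. State for each score which trials enter it.

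The sponsor should confirm that the platform output retains no-go errors by cue. If it does, the cost is about one sentence, with no new procedure, visit or participant burden. The change is best made before any comparison between groups is run.
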